4.3.3 Secondary and Exploratory Outcomes Analyses

For secondary and exploratory outcomes, Table 1 and Table 2 display the statistical model and intervention effects according to outcome type (binary, continuous, time to event).

For binary outcomes, logistic regression models will be used to estimate odds ratios with 95% CIs. For count outcomes, Poisson or negative binomial regression models (if overdispersion is suggested by the data) will be used to estimate rate ratios with 95% CIs.

For continuous outcomes, linear (or another more outcome-specific distribution) regression models will be built.

For change in continuous outcomes from baseline to 30-days post-discharge, we will consider analysis of covariance (ANCOVA), adjusting for the baseline outcome value.

For time in days to re-admission or all-cause mortality after discharge, a survival analysis will be performed. Cumulative event rates will be calculated with the Kaplan-Meier method, with event or censoring times calculated from the date of discharge. Differences in Kaplan-Meier survival curves between the study arms will be assessed using the log-rank test. The Cox proportional hazards model will estimate the hazard ratio with 95% CI.

Multiple testing correction for p-values will be applied in the analyses of secondary outcomes using the Holm method.

For exploratory outcomes, in addition to 95 % CIs, we will also report p-values, since we agree with Pocock et al. (2021) that such p-values, although mostly characterized as being a form of descriptive statistics, can "help the reader focus on potentially important exploratory findings."

Table 1. Secondary Outcomes, Statistical Models and Measures of Intervention Effect by Outcome Type

Secondary Outcome	Outcome Type	Model	Intervention Effect (Unadjusted)
Number of ED visits within 30 days post-discharge	Count ≥0	Poisson or negative binomial regression including intervention arm indicator	Rate ratio with 95% CI, and p-value*
Number of ED visits within 90 days post-discharge	Count ≥0	Poisson or negative binomial regression including intervention arm indicator	Rate ratio with 95% CI, and p-value*
Composite of re-admission or all-cause mortality within 30 days post-discharge	Binary, 0/1	Logistic regression including intervention arm indicator	Odds ratio with 95% CI, and p-value*

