Composite of re-admission or all-cause mortality within 90 days post-discharge	Binary, 0/1	Logistic regression including intervention arm indicator	Odds ratio with 95% CI, and p-value*

CI: confidence interval; ED: emergency department

^{*}Multiple testing correction for p-values will be applied using the Holm method.

Table 2. Exploratory Outcomes, Statistical Models and Measures of Intervention Effect by Outcome Type

Exploratory Outcome	Outcome Type	Model	Intervention Effect (Unadjusted)
Leaving against medical advice at discharge	Binary, 0/1	Logistic regression	Odds ratio with 95% CI, and p-value
Self-reported quality of care transition after hospital discharge (CTM-3) at the time of the 30-day interview	Continuous, range 0-100, unknown distribution	Linear regression or appropriate model for specific distribution type	Mean difference with 95% CI, and p-value
Self-reported change in difficulties meeting subsistence needs total score (Competing Priorities) at the 30-day interview post discharge relative to baseline, total score	Continuous, range 0-15	ANCOVA on change in total scores, with baseline value as covariate	Mean difference with 95% CI, and p-value
For participants who did not previously report contact with a case manager in the 30 days prior to the baseline interview, connection to a case manager in the community at the time of the 30-day interview	Binary, 0/1	Logistic regression	Odds ratio with 95% CI, and p-value
Medication adherence (MMAS-8) at the time of the 30-day interview	Continuous, range 0-8	Linear regression or appropriate model for specific distribution type	Mean difference with 95% CI, and p-value
Change in health status EQ-5D-3L at the time of the 30-day interview relative to baseline	Continuous, range -0.340 to 1.0 at each time point	ANCOVA on change in total scores, with baseline value as covariate	Mean difference with 95% CI, and p-value
Change in quality of life EQ-5D VAS at the time of the 30-day interview relative to baseline	Continuous, potential range 0-100	ANCOVA on change in total scores, with baseline value as covariate	Mean difference with 95% CI, and p-value
Days spent in hospital post-discharge within 90 days post-discharge	Count ≥0	Poisson or negative binomial regression including intervention arm indicator	Rate ratio with 95% confidence interval, and p-value

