4.3.5 Sensitivity Analyses

For the primary outcome, we will evaluate whether a sensitivity analysis needs to be performed excluding the 16 patients who were asked the 3 original questions about visiting a PCP within 14 days. Determination will depend on whether, for these cases, the only indicator of the visit was by self-report.

For the Competing Priorities exploratory outcome, we will also compare groups using 3 alternative scoring methods. The first method calculates, for each participant, the mean score across all 5 items, range 1-4 (each item is scored on a 1–4 scale, with Never = 1; Rarely = 2; Sometimes = 3; and Usually = 4). The second method dichotomizes the mean score to participants with frequent (>3) versus infrequent (≤3) competing priorities. The third method classifies participants as having competing priorities if they responded "Usually" to any of the 5 items. For the first method, we will fit an analysis of variance (ANOVA) model. For the binary outcomes, we will fit generalized estimating equations, for the binomial distribution with logit link. Models will include the intervention arm indicator, time (30-day versus baseline interview), and the interaction of intervention arm by time. A significant interaction will indicate that the change from baseline is different between the study groups.

The total MMAS-8 score can also be categorized into three levels of adherence: high adherence (score = 8), medium adherence (score of 6 to < 8), and low adherence (score< 6). We will compare the groups using the Cochran-Armitage test for trend.

For binary outcomes outlined in Tables 1 and 2, and subgroup analyses, we will also fit modified Poisson regression models to estimate risk ratios with 95% CIs. All analyses will be conducted using R, STATA, and SAS. All statistical tests will be two-sided and a p-value of 0.05 or less will indicate statistical significance.

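### The alternative Competing Priorities scorings are tested by an arm-by-time interaction, a valid test but less efficient than the baseline adjustment used for the main score, and one that changes model and scoring together

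*SAP*

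**What the plan says.** Section 4.3.3 sets the approach for change scores: "For change in continuous outcomes from baseline to 30-days post-discharge, we will consider analysis of covariance (ANCOVA), adjusting for the baseline outcome value". Table 2 applies it to the Competing Priorities total (0–15): "ANCOVA on change in total scores, with baseline value as covariate".

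Section 4.3.5 then adds three other scorings of the same five items as sensitivity analyses. One is the item mean (range 1–4): "For the first method, we will fit an analysis of variance (ANOVA) model". One is a cut of that mean: "The second method dichotomizes the mean score to participants with frequent (>3) versus infrequent (≤3) competing priorities". The last flags anyone who answers Usually to at least one item. For these last two, "For the binary outcomes, we will fit generalized estimating equations, for the binomial distribution with logit link". The terms are then listed: "Models will include the intervention arm indicator, time (30-day versus baseline interview), and the interaction of intervention arm by time". The reading rule follows: "A significant interaction will indicate that the change from baseline is different between the study groups".

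The sentence on model terms comes after both the ANOVA and the GEE sentences, so it appears to govern both. Baseline enters as a repeated outcome, not as a covariate. The SAP gives no reason for leaving the Table 2 approach.

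**The concern.** Randomisation makes the arms equal at baseline in expectation. The interaction subtracts the observed baseline difference in full, which adds baseline sampling noise without removing any bias. Regression on baseline subtracts only the share that predicts the 30-day value.

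The purpose of these analyses is to show whether the Competing Priorities result survives other ways of scoring the instrument. Here the scoring and the model change at the same time. If a binary scoring is non-significant where the main ANCOVA is significant, the reader cannot tell whether the scoring or the weaker test is responsible.

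**Working it through.** **Inputs from the SAP.** 256 evaluable per arm, 32% versus 44%, 80% power, 20% attrition (4.1); two-sided 0.05 (4.3.5); 1:1 allocation (1.1). The SAP has no power or precision figure for the Competing Priorities analyses.

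**Assumed, because the SAP does not give them.** 256 complete baseline/30-day pairs per arm (borrowed from 4.1); ρ from 0.2 to 0.7; baseline prevalence of 50%, 30% or 20%; and the effect sizes below.

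**Step 1. The SAP's own sample size.** With p̄ = 0.38,

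n = [1.960·√(2·0.38·0.62) + 0.842·√(0.32·0.68 + 0.44·0.56)]² / 0.12² = (1.345 + 0.573)² / 0.0144 ≈ 256 per arm.

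Then 256/0.8 = 320 per arm, 640 in total. Both figures reproduce.

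**Step 2. Linear scale.** With equal variance σ² at both times and n per arm:
- difference in change: (2/n)·2σ²(1−ρ)
- baseline-adjusted difference: (2/n)·σ²(1−ρ²)
- ratio: 2(1−ρ)/(1−ρ²) = 2/(1+ρ), above 1 for every ρ below 1

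Relative to a 30-day comparison that ignores baseline, the ratio is 2(1−ρ). Below ρ = 0.5 the interaction is therefore less precise than not using baseline at all.

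**Step 3. Binary scale, by simulation.** With complete pairs the GEE interaction equals the between-arm difference in change of log-odds. Each arm contributes variance 1/(n·p₀q₀) + 1/(n·p₁q₁) − 2c/(n·p₀q₀p₁q₁), where c is the covariance of the two binary values. The comparator is logistic regression of 30-day status on arm and baseline status. Baseline is 50% in both arms and 30-day prevalence is 50% versus 38% (4,000 trials per row; variance ratio on the marginal log-odds scale):

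| ρ | 2/(1+ρ) | Simulated variance ratio | Power, interaction | Power, 30-day only | Power, baseline-adjusted |
|---|---|---|---|---|---|
| 0.2 | 1.67 | 1.60 | 59.5% | 77.7% | 79.4% |
| 0.3 | 1.54 | 1.53 | 66.4% | 79.9% | 83.7% |
| 0.5 | 1.33 | 1.34 | 80.2% | 78.0% | 89.5% |
| 0.7 | 1.18 | 1.17 | 95.1% | 77.6% | 97.3% |

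Repeat simulations differ from these by no more than about 3 points.

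At lower prevalence, interaction against baseline-adjusted, for ρ = 0.2 / 0.3 / 0.5 / 0.7:
- 30% versus 20%: 56.7 / 62.2 / 77.6 / 94.2% against 76.1 / 78.6 / 85.6 / 95.7%
- 20% versus 12%: 54.0 / 59.5 / 72.5 / 92.6% against 71.8 / 73.3 / 80.6 / 93.9%; variance ratios 1.48, 1.35, 1.19 and 1.05

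With no effect (50% throughout), rejection was 4.7–5.6% for the interaction and 4.5–5.4% for the adjusted model.

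**Step 4. Scale of the estimate.** At ρ = 0.5 (50% versus 38%), the mean log odds ratio and its SD were:
- interaction: −0.494, SD 0.176 (ratio 2.81)
- conditional adjusted: −0.663, SD 0.207 (ratio 3.20)
- adjusted and standardised to a marginal odds ratio: −0.492, SD 0.153 (ratio 3.22)

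The conditional odds ratio has the larger raw SD but the stronger test. The standardised one estimates the same quantity as the interaction, more precisely.

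**Step 5. The mean score.** Appendix 2 rescales each item from 1–4 to 0–3 and sums. With all five items answered, total = 5 × (mean − 1): a mean of 1 gives 0 and a mean of 4 gives 15. Under the Table 2 ANCOVA the mean score would give one fifth of the effect and the same p-value. Any difference in significance from the main analysis would then come from the model alone.

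**The case against.** The strongest reply is that nothing here is invalid. The outcome is defined as change from baseline (2.3.2), the interaction tests exactly that, and type I error is near 5% with complete data. The loss shrinks to 1–2 points of power at ρ = 0.7 and depends on assumed values. Dichotomising loses information in any case, so a baseline-adjusted binary analysis could still disagree with the main one. All of this stands. It limits the importance of the point but does not remove it: Table 2 also calls its outcome a change and adjusts for baseline, and under randomisation both approaches target the same marginal contrast (step 4).

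Three stronger readings are tempting, and the SAP does not support them.

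- A reader might infer that arm-dependent dropout makes the GEE test reject too often. In a simulation with 320 per arm, 50% prevalence and dropout of 35% versus 15% among those with baseline difficulty (20% otherwise), rejection under no effect at ρ = 0.3 and 0.5 was 7.3% and 11.7% with an independence working correlation. With an exchangeable one and the same interaction it was 4.9% and 4.5%. The SAP names no working correlation, so the inflation comes from an added assumption, not from testing an interaction. Section 4.4.3 also plans multiple imputation for these self-reported outcomes.
- A reader might infer that the ANOVA treats a participant's two interviews as independent. The SAP is silent on a participant term, and an ANOVA with a time factor is naturally a repeated-measures one. Silence is not a specification.
- A reader might take the modified Poisson models as already covering these scorings. Section 4.3.5 plans them for binary outcomes in Tables 1 and 2 and for subgroup analyses; Table 2 lists Competing Priorities only as continuous.

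**Conclusion.** The point holds as one of efficiency and interpretability. Under the assumed 256 complete pairs per arm, and across the three prevalence settings, the planned interaction gives up about 18–20 points of power at ρ = 0.2, 8–9 at ρ = 0.5 and 1–2 at ρ = 0.7. The true position in that range is unknown, since the SAP states neither the correlation nor the prevalence. The change of model also prevents the scorings from being compared like for like, most plainly for the mean score. Importance is low: these are sensitivity analyses of one exploratory outcome, and no primary or secondary analysis is affected.

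**What to change.** Revise section 4.3.5 as follows.

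- **Two binary scorings:** fit logistic regression of 30-day status on arm, adjusted for baseline status. State whether the reported effect is the conditional odds ratio or a standardised marginal one, with 95% CI. Alternatively, keep the two-time-point GEE, constrain the arms to be equal at baseline, and name a working correlation other than independence.
- **Mean score:** use the Table 2 ANCOVA form.
- **Optional:** a baseline-adjusted risk ratio from modified Poisson regression, written in as an addition.

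The cost is a change of wording, with no new data or software. There are two small downsides. Participants without a baseline answer leave these models, as they already do in the main ANCOVA. An adjusted odds ratio is conditional unless standardised, so it should not be set beside a marginal one without saying so.

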4.4 Handling of Incomplete Data

Missing data in outcomes may lead to biased estimates of the intervention effect and/or loss of power to test the intervention effect. In general, if rates of missingness per variable are low (< 5% overall), we may consider complete case analysis (Graham, 2009).

4.4.1 Missing Data for the Primary Outcome, Mortality, and Healthcare Utilization Outcomes

We expect that there will be no missing data for our primary outcome, since we are using 3 sources of data. We expect likewise for all secondary outcomes and for exploratory outcomes related to death or healthcare utilization.

4.4.2 Missing Data for Baseline Variables and 30-Day Interview Self-Reported Exploratory Outcomes

The main reasons for missing data at baseline include "do not know" responses or refusal to answer survey questions.

Missing data reasons at the 30-day interview include the same reasons as at baseline, but also may be due to patients dying after discharge and before the interview, being lost to follow-up, refusing the interview, or being too medically unwell to participate in interviews.

For most of the exploratory outcomes, missing data may be missing not at random (MNAR). This occurs when the distribution of missing data depends on unobserved characteristics of the individuals, in particular, the outcomes themselves (i.e., missing because of lower medication adherence, lower quality of life, leaving against medical advice, etc.). For data that are missing at random (MAR), the probability of missingness depends only on observed data but not on the data that are missing (Austin, 2018). That is, after controlling for or stratifying by observed variables, missingness is random. There is general consensus that the greater the number of observed variables that can be assumed to capture reasons for (or associated with) missingness and can be incorporated in the multiple imputation process, the more plausible the MAR assumption becomes (Collins et a., 2001, Graham, 2012, White, 2010). The traditional approach for handling missing data is multiple imputation, and multiple imputation can handle MAR and specific MNAR scenarios (van Buuren, 2018).

Appendix 1. Outcome Definitions

1 Primary Outcome

The primary outcome will be determined using participant self-report at the 30-day interview, PCP office confirmation, and administrative databases

Participant self-report at the 30-day interview was originally determined using the following 3 questions:

Q1 "Do you have a regular family doctor?" By family doctor, we mean a family doctor, GP, or a nurse practitioner who is familiar with you.

Q2 If Yes: Have you seen your primary care provider since you were discharged from St. Michael's Hospital or St. Joseph's Hospital on [DATE]?

Q3 If Yes: What was the date of the first visit with your primary care provider after discharge?

These 3 previous questions were only asked for the first 16 participants, and then were revised as follows and retained until the end of the study:

Q1 Have you seen any doctor or nurse practitioner since you were discharged from St. Michael's Hospital or St. Joseph's Hospital on [DATE]?

Q2 If Yes: Have you seen a family doctor or nurse practitioner since you were discharged from St. Michael's Hospital or St Joseph's Hospital on [DATE]?

Q3 If Yes: What was the date of the first visit with the family doctor or nurse practitioner after discharge?

The primary outcome uses participant self-report at the 30-day interview, which will be defined as follows:

If the interval between discharge date and date of first visit with primary care provider, family doctor, or NP is less than or equal to 14 days then follow-up with a PCP within 14 days of hospital discharge is equal to 1 (Yes). Otherwise, it is equal to 0 (No).

2 Secondary Outcomes

Secondary outcomes will be determined using administrative databases

- 1. Number of emergency department visits within 30 days post-discharge
- 2. Number of emergency department visits within 90 days post-discharge
- 3. Composite measure of any re-admission or all cause-mortality* within 30 days post-discharge
- 4. Composite measure of any re-admission or all cause-mortality* within 90 days post-discharge

*Readmissions and days in hospital (i.e., acute care utilization) outcomes will not include labour and delivery visits, and planned readmissions.

Transfers within and between hospitals may count as single admission events, but will be determined on a case-by-case situation. For example, if a patient is transferred between services within the hospital, the entire hospital stay will be treated as a single admission.

Counting the number of transfers will be formalized after careful review of the literature and based on the frequency of inter- vs intra-hospital transfers.

3 Exploratory Outcomes

Exploratory outcomes will be collected using 3 sources: hospital discharge summaries, participant self-report at the 30-day interview, and administrative databases.

3.1 Hospital Discharge Summaries

1. Indicator of participant leaving against medical advice at discharge

3.2 Participant Self-Report at 30-Day Interview

- 1. Self-reported quality of care transition (3-item Care Transitions Measure, CTM-3) after hospital discharge at the time of the 30-day interview
- 2. Self-reported change in difficulties meeting subsistence needs (Competing Priorities measure from RAND Course of Homelessness Study) at the time of the 30-day interview relative to baseline
- 3. For participants who did not previously report contact with a case manager in the 30 days prior to the baseline interview, connection to a case manager in the community at the time of the 30-day interview
- 4. Medication adherence (eight-item Morisky Medication Adherence Scale, MMAS-8) at the time of the 30-day interview
- 5. Change in health status (EQ-5D-3L; European Quality of Life Five Dimension Three Levels) at the time of the 30-day interview relative to baseline

6. Change in quality of life (EQ-5DVisual Analogue Scale) at the time of the 30-day interview relative to baseline

3.3 Administrative Databases

- 1. Total number of days spent in hospital (s) post-discharge within 90 days post-discharge
- 2. Total number of days spent in hospital (s) post-discharge within 180 days post-discharge
- 3. Time in days to all-cause re-admission or mortality after discharge (up to 180 days post-discharge)
- 4. Attendance of any non-PCP healthcare appointment made by the time of discharge* within 180 days post-discharge
 - *Only non-PCP appointments made by the time of discharge and documented in the discharge summary will be assessed for attendance

A summary of outcome domains and study instruments and detailed descriptions of study instruments are provided in Liu et al, 2022 and its online supplemental file 3.

Appendix 2 Self-Reported Measures and Scoring Algorithms

Details of the instruments used to evaluate exploratory self-reported outcomes are described below:

1 CTM-3: Three-Item Care Transitions Measure

The CTM-3 is a measure designed to evaluate the extent to which patients believe the healthcare team accomplished essential care processes in preparing them for discharge and participating in post-hospital self-care activities. This measure was endorsed by The National Quality Forum (www.qualityforum.org).

Each of the three items is scored on a 1–4 scale, with Strongly Disagree=1; Disagree=2; Agree=3; and Strongly Agree=4. For each participant, the mean score is calculated by summing up the responses across the 3 items and dividing by the number of items answered (https://mhdo.maine.gov/pdf/NQF_CTM_3_%20Specs_FINAL.pdf).

The mean score (mean_ctm3) is then re-scaled to a 0-100 score (CTM3_score) using the following formula:

```
CTM3_score=(new_max - new_min) / (old_max - old_min) * (mean_ctm3 - old_min) + new_min,
```

where new max=100; new min=0; old max=4; old min=1.

Higher scores indicate better care transition experiences. This continuous variable has been used in a variety of studies.

2 Competing Priorities

This measure is a validated 5-item measure of frequency of difficulty in meeting the following needs over the past 30 days: shelter, food, clothing, a place to wash, and access to a bathroom (Koegel et al, 1996; Gelbert et al, 1997).

Each item is scored on a 1–4 scale, with Never=1; Rarely=2; Sometimes=3; and Usually=4. There is no consensus on how to best score this instrument. We are aware of four scoring methods.

The first method calculates, for each participant, the mean score across all 5 items (Koegel et al, 1996, range 1-4).

The second method dichotomized the mean score to participants with frequent (>3) versus infrequent (≤ 3) competing priorities (Gelbert et al, 1997).

The third method classifies participants as having competing priorities if they responded "Usually" to any of the 5 items (Hwang et al, 2010).

The fourth method, re-scales items to a range of 0 to 3, and calculates the total score as their sum (Baggett et al, 2018, range 0-15).

3 MMAS-8: Eight-Item Morisky Medication Adherence Scale (purchased license to use)

The MMAS-8 is a validated self-reported measure of medication adherence that has been validated among disadvantaged patient populations and those with chronic illnesses. The MMAS-8 consists of 8 items, 7 of which are yes/no questions, coded as 1 if indicating adherence or 0 if otherwise. The last item has a five-point Likert-scale rating, with Never/Rarely=1; Once in a while=0.75; Sometimes=0.50; Usually=0.25; and All the time=0.

For each participant, the total score is calculated as the sum of all items (range 0-8). Higher scores indicate greater adherence. The total score can also be categorized into three levels of adherence: high adherence (score = 8), medium adherence (score 6 to < 8), and low adherence (score < 6).

4 EQ-5D: EuroQoL-5D

The EQ-5D instrument was originally developed to include two parts to measure health status and quality of life: the 3L and the visual analog scale (VAS).

The EQ-5D-3L is a generic measure of health-related quality of life that has been widely used among homeless populations. The EQ-5D-3L includes five items concerning mobility, self-care, usual activities, pain/discomfort, and anxiety/depression, which are coded as 1, 2, or 3 ordered according to problem/disability level. The scoring for the 3L portion is unique to each country based on the "value" ascribed to that health state by a representative sample of the population. We will use the validation for Canada

The combination of values from all items are scaled into a value according to Table A1 [range -0.340 (33333) to 1 (11111).

Table A1. List of values for all health states derived from EQ5D-L in Canada*

Health state	Value	Health state	Value	Health state	Value
11111	1.000	21111	0.843	31111	0.567
11112	0.826	21112	0.780	31112	0.504
11113	0.609	21113	0.563	31113	0.286
11121	0.844	21121	0.799	31121	0.522
11122	0.781	21122	0.736	31122	0.459
11123	0.564	21123	0.518	31123	0.242
11131	0.591	21131	0.546	31131	0.269
11132	0.528	21132	0.483	31132	0.206
11133	0.311	21133	0.265	31133	-0.011
11211	0.817	21211	0.771	31211	0.495
11212	0.754	21212	0.708	31212	0.432
11213	0.537	21213	0.491	31213	0.214
11221	0.772	21221	0.727	31221	0.450
11222	0.709	21222	0.664	31222	0.387
11223	0.492	21223	0.446	31223	0.170
11231	0.519	21231	0.474	31223	0.197
11231	0.456	21232	0.411	31232	0.134
11232	0.239	21233	0.193	31232	-0.083
11311	0.784	21311	0.738	31311	0.461
11311	0.720	21312	0.675	31312	0.398
11312	0.503	21312	0.458	31313	0.181
11313	0.739	21313	0.693	31321	0.417
11321	0.676	21321	0.630	31322	0.354
11323	0.459	21323	0.630	31323	0.136
11323	0.486	21323	0.440	31323	0.130
11331	0.480	21331	0.377	31332	0.104
11332	0.206	21332	0.160	31333	-0.117
12111	0.819	22111	0.773	32111	0.496
12111	0.755	22111	0.710	32111	0.433
12112	0.733	22112	0.493	32112	0.433
12113	0.338	22121	0.728	32113	0.452
12121	0.711	22121	0.728	32121	0.389
12122	0.494	22123	0.448	32122	0.171
12123	0.521	22123	0.475	32123	0.171
12131	0.321	22131	0.412	32131	0.136
12132	0.438	22132	0.412		-0.082
12133					
12211	0.746	22211 22212	0.701	32211 32212	0.424
12212	0.683		0.638		0.361
	0.466	22213	0.420	32213	0.144
12221	0.702	22221	0.656	32221	0.380
12222	0.639	22222	0.593	32222	0.316
12223	0.421	22223	0.376	32223	0.099
12231	0.449	22231	0.403	32231	0.127
12232	0.386	22232	0.340	32232	0.063
12233	0.168	22233	0.123	32233	-0.154
12311	0.713	22311	0.668	32311	0.391
12312	0.650	22312	0.604	32312	0.328
12313	0.433	22313	0.387	32313	0.111
12321	0.669	22321	0.623	32321	0.346
12322	0.605	22322	0.560	32322	0.283

12323	0.388	22323	0.343	32323	0.066
12331	0.416	22331	0.370	32331	0.093
12332	0.352	22332	0.307	32332	0.030
12333	0.135	22333	0.090	32333	-0.187
13111	0.665	23111	0.620	33111	0.343
13112	0.602	23112	0.557	33112	0.280
13113	0.385	23113	0.339	33113	0.063
13121	0.621	23121	0.575	33121	0.298
13122	0.557	23122	0.512	33122	0.235
13123	0.340	23123	0.295	33123	0.018
13131	0.368	23131	0.322	33131	0.045
13132	0.304	23132	0.259	33132	-0.018
13133	0.087	23133	0.042	33133	-0.235
13211	0.593	23211	0.548	33211	0.271
13212	0.530	23212	0.484	33212	0.208
13213	0.313	23213	0.267	33213	-0.010
13221	0.549	23221	0.503	33221	0.226
13222	0.485	23222	0.440	33222	0.163
13223	0.268	23223	0.223	33223	-0.054
13231	0.296	23231	0.250	33231	-0.027
13232	0.232	23232	0.187	33232	-0.090
13233	0.015	23233	-0.030	33233	-0.307
13311	0.560	23311	0.514	33311	0.238
13312	0.497	23312	0.451	33312	0.174
13313	0.279	23313	0.234	33313	-0.043
13321	0.515	23321	0.470	33321	0.193
13322	0.452	23322	0.407	33322	0.130
13323	0.235	23323	0.189	33323	-0.087
13331	0.262	23331	0.217	33331	-0.060
13332	0.199	23332	0.154	33332	-0.123
13333	-0.018	23333	-0.064	33333	-0.340

^{*}Source: Bansback N, Tsuchiya A, Brazier J, Anis A. Canadian valuation of EQ-5D health states: preliminary value set and considerations for future valuation studies. PLoS One. 2012;7(2):e31115.
